3.2.2 Viscoseal (intervention) arm

Apart from the difference in terms of Viscoseal administration to the intervention group, the surgical protocol for the Viscoseal arm is identical to that of the standard care group. At the end of the surgery, again all the remaining fluids are drained from the knee, but this is followed by injection of 10 mL of Viscoseal preparation. Used Viscoseal product and syringes will be disposed of in line with local guidelines on disposal of clinical waste.

3.2.3 Magnetic Resonance Imaging

A subset of 24 participants will also undergo an additional MRI at 26 post-surgery to determine the morphology and status of the meniscus radiologically. This MRI will be as the one that all patients undergo as part of diagnosing the meniscal injury prior to surgery. Apart from consenting to the MRI sub-study as part of HIKE, patients will also provide consent separately for the MRI procedure itself. The protocol for meniscus imaging has been described previously [24]. A 1.5-Tesla Siemens Avanto scanner will be used for this purpose to obtain sagittal T1, sagittal PDFS, coronal STIR, coronal PDFS and axial T2 GRE images.

4. STUDY HYPOTHESIS

4.1 Primary objective

• To assess the efficacy of Viscoseal for reduction of post-operative pain after arthroscopic meniscal repair surgery when compared with standard care.

IRAS ref 272362 Page **10** of **30**

4.2 Secondary objective

- To assess the efficacy of Viscoseal for reduction of post-operative swelling after arthroscopic meniscal repair surgery when compared with standard care.
- To assess the efficacy of Viscoseal for improvement of post-operative patient-reported outcome measures, including pain upon walking and knee functionality, after arthroscopic meniscal repair surgery when compared with standard care.
- To evaluate, as part of a pilot sub-study, if there are any differences in terms of meniscus and knee joint recovery by means of radiological examination using MRI

5. STUDY PROTOCOL

5.1 Study design, recruitment sites and timeline

This concerns a single-centre, controlled prospective randomized study of CE-marked medical devices. The study will be carried out in the following NHS Trust:

- North Cumbria University Hospitals NHS Trust, both Cumberland Infirmary, Carlisle, and West Cumberland Hospital, Whitehaven. CI/PI [name]

The study will take place in a hospital setting with support and oversight from the treating orthopaedic surgeon, nursing staff and research staff. Where appropriate, research delivery staff will be delegated to provide support with data collection and processing.

Table 1. Anticipated timeline

Month	Setup	Recruitment	Analysis	Finalise
Oct-19	Submission for HRA approval			
Dec-19	NIHR portfolio adoption			
Dec-19	HRA and Trust approval			
Jan-20		Start recruitment		
Jul-22		Finish recruitment		
Jan-23			Follow-up complete; Analyse data.	
Feb-23				manuscript & report writing complete

5.2 Participant identification and research setting

Participants will be recruited from orthopaedics clinics and all eligible patients will be invited to take part until the required numbers have been achieved. Identification will be by the orthopaedics

IRAS ref 272362 Page **11** of **30**

clinical team, who are supporting the study. A screening form will be completed for potentially eligible patients to confirm that they indeed meet the trial criteria.

To summarise, the orthopaedic team will:

- Identify potentially eligible patients and ask verbal consent for them being approached about the study by a member of the R&D team
- Complete the incl/excl criteria part of the screening form (if a patient has given verbal consent to being approached by the research team then they can complete the screening form)

5.3 Consent and recruitment

Those eligible will be approached and provided with an information pack and consent form, which will be signed to indicate that informed consent has been given. Patients will be given ample time to consider taking part, more than 24 hours if they wish. The study will be first mentioned at an orthopaedics out-patient clinic visit. The direct healthcare professional will first approach a patient about the study, and after verbal consent by the patient the healthcare professional themselves or a member of the research team can go through the informed consent process.

Patients are also allowed to consent to taking part when first approached as long as the study has been discussed with the patient and they have been given time to read the patient information leaflet and opportunity to ask any questions that they may have. Participants will receive no incentives and consent will be regarded as a process and not a one-off event. Participants are free to withdraw from the study at any time without the need to give any reasons for withdrawal. Their standard of care will not be affected by either declining to participate in the study or withdrawing during participation. Data collected up to the date of withdrawal will be retained for analysis.

Participants will be randomised to either the treatment as usual (TaU) or the intervention group (Viscoseal) any time up until the day of surgery. Study subjects who subsequently require additional significant surgical intervention, primarily ligament reconstruction, will be withdrawn from the study.

The MRI sub-study will be offered to all patients consecutively, and this will be done until the 24 required patients for said sub-study have been recruited.

5.4 **Follow-up**

Patients are in the study for a period of 26 weeks. Thereafter, the patient will be followed up as they would be in normal clinical practice. Two study follow-up visits are aligned to hospital/clinic visits and the other are done remotely. Baseline data can be collected on the day of surgery (prior the actual operation), and 48 hrs, 7 days, 14 days and 12 weeks post-surgery data can be collected when the patient attends for standard follow-up in the orthopaedics out-patient department. The data at week 26 falls outside these dates. In these instances, data can be collected over the phone, via e-mail or by mail (whichever is preferred by the patient – mail is by use of freepost, to avoid patients incurring any costs). The researcher will ask/phone/e-mail/mail the participant at each follow-up time point to check on any adverse event reporting, and if consented by the patient can

IRAS ref 272362 Page **12** of **30**

also send reminders to the participant regarding the completion of certain outcome data at the aforementioned follow-up time points.

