Hyaluronate [Viscoseal] Injection after Knee surgery; an Evaluation

A multi-centre, randomised, single-blinded trial assessing patient and clinical outcomes of Viscoseal injection after meniscal repair surgery

Version 1.3, dd 21 May 2021

Chief Investigator's Statement of Ownership and Content.

I, [name], confirm that this protocol is my work and is owned by me. The protocol conforms with standards outlined in the Declaration of Helsinki 1964.

Name (PRINT):______
Signature:_____
Date: _____

IRAS ref 272362 Page **1** of **30**

RESEARCH PROTOCOL SUMMARY

TITLE:	A multi-centre, randomised, single-blinded trial assessing
	patient and clinical outcomes of Viscoseal injection after
	meniscal repair surgery
Short title:	HIKE trial (Hyaluronate [Viscoseal] Injection after Knee surgery; an
IDAC mumahan	Evaluation)
IRAS number	272362
Device description	'Viscoseal' , a 0.5% sodium Hyaluronate solution in a
	10 ml bottle. To be administered intra-articularly.
	Active ingredient - Sodium hyaluronate
	Excipients - Sodium chloride, Sodium
	monohydrogenphosphate, sodium dihydrogenphosphate,
	water for injection.
	Duration of treatment: Single instillation at the end of
	arthroscopy and after completion of normal irrigation process.
	Current usage: Licensed and widely used throughout the UK
	and Europe for arthroscopic procedures. Viscoseal is devoid of
C. I.	animal proteins and hence has negligible allergenic potential.
Study type	Medical device randomised controlled trial, involving CE-
	marked devices used for intended purpose.
Study design	Single-centre, two-arm (1:1 allocation), single-blinded,
	prospective randomized trial.
Patient population	Total of 52 patients, aged 18-59 and BMI < 35, with MRI-
	confirmed meniscal injury who are eligible for meniscal repair
	surgery due to associated pain and impaired knee joint
	functionality. Previous knee surgery on index leg,
	accompanying ligament injury, and advanced knee
	osteoarthritis are the main exclusion criteria.
	For MRI imaging pilot sub-study, a total of 24 patients (out of
	the above 52 patients) will be enrolled.
Primary objective	To assess the efficacy of Viscoseal for reduction of post-
,,	operative pain after arthroscopic meniscal repair surgery
	when compared with standard care.
Secondary objectives	To assess the efficacy of Viscoseal for reduction of post-
	operative swelling after arthroscopic meniscal repair surgery
	when compared with standard care.

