3.2 Intervention

3.2.1 Standard care (control) arm

All patients receive general anesthesia and a pneumatic tourniquet is used. Patients are already randomised prior to surgery to avoid delays with surgery and allow a vial of Viscoseal to be ready for the relevant patients. Joint irrigation is performed with the assistance of a manual arthroscopic pump using 0.9% NaCl solution at room temperature. Then, the remaining fluids are drained from the knee. At the end of the surgery, local anaesthetics is applied to the soft tissue of the arthroscopic portals [either 20 ml 0.5% Levobupivacaine (Chirocaine®), or 20 ml 0.75% Ropivocaine (Naropin®), or equivalent product], and the knee is dressed, while the tourniquet is still inflated. All surgeries are intended to be performed in a day-surgery facility with the patient being discharged the same day. Postoperatively, partial weight bearing with crutches is allowed. Crutches are recommended for the first 48 hours, primarily for patient safety by minimising the risk of a fall.

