6.3 Early withdrawal of subjects

Patients have the right to withdraw from the trial at any time and without giving any reason. If a patient withdraws from the trial, any and all information gathered prior to the withdrawal will be excluded in the analysis, no further data collection will occur. If a patient does not attend a planned follow-up appointment then two more attempts will be made to contact the patient regarding the study. If still no contact can be made then the patient is deemed lost to follow-up and any collected study data will be retained.

As mentioned in section 5.3, study subjects who subsequently require additional significant surgical intervention, primarily ligament reconstruction, will be withdrawn from the study.

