8. STATISTICAL CONSIDERATION AND DATA ANALYSIS PLAN

8.1 Analysis of baseline characteristics

To determine the demographics and characteristics of the patients in the two arms the following data will be collated:

- Age (yrs)
- Gender

IRAS ref 272362 Page **18** of **30**

• Height (kg), weight (cm), BMI

Distribution of data will be summarised but no inferential statistics will be applied in line with guidance [26].

Data concerning the actual meniscal repair procedure will also be collected, including:

- Exact meniscal surgery carried out (repair, partial meniscectomy, complete meniscectomy)
- Length of operation (min) and blood loss (ml) during operation
- Details on lavage procedure, if deviation from standard procedure.
- Type of anaesthetic and analgesics prescribed post-surgery
- Hospital length of stay (days)
- Moment physiotherapy and early recovery initiated, if applicable
- Any analgesics and/or anti-inflammatories administered and/or prescribed.

Any differences in distribution will be established with Chi-squared test or Mann-Whitney U-test/t-test (depending on distribution of data) as indicated.

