8.3 Secondary outcome statistics

The average baseline demographics for participants in each group will be compared to ascertain that randomisation has indeed led to comparable distribution of participants:

Sex, age, height, weight, BMI, length of stay, type of anaesthetic for surgery and type of analgesics post-surgery.

To compare outcomes between the two groups (standard vs Viscoseal), student t-test, Mann-Whitney U-test or Chi-squared test will be applied as applicable, depending on type and distribution of data .

IRAS ref 272362 Page **19** of **30**

Cox proportional hazards regression analysis will be conducted to investigate the role of Viscoseal and other covariates (as mentioned above) in post-surgery related pain, swelling and knee function.

The statistics apply to:

At least 2 weeks prior to surgery, and 7 days and 14 days post-surgery

- Indication of degree of swelling by measurement of thigh, suprapatellar and calf girth.

Up to 12 weeks prior to surgery, 12 weeks and 26 weeks post-surgery, knee function measurements: Lysholm and WOMET tools.

Descriptive safety overview post-surgery up to 26 weeks:

- Readmitted to theatre and/or hospital
- Infection of wound site
- Diagnosed with pulmonary embolism or deep vein thrombosis.

Patient satisfaction survey at 12 weeks and 26 weeks post-surgery – any difference in outcome will be determined with Mann-Whitney U-test

MRI diagnostics outcomes:

Descriptive statistics, primarily frequencies and averages, to summarise per intervention arm

- Type of injury
- Size of injury
- Grading of injury
- Any recurring or new meniscal injury

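### Sections 5.3 and 6.3 withdraw randomised patients who need further significant surgery and contradict each other on whether their data are kept; withdrawal also conflicts with the 26-week readmission outcome in section 8.3

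*Protocol*

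**What the plan says.** **Withdrawal rule.** Section 5.3: "Study subjects who subsequently require additional significant surgical intervention, primarily ligament reconstruction, will be withdrawn from the study." Section 6.3 repeats it with a cross-reference: "As mentioned in section 5.3, study subjects who subsequently require additional significant surgical intervention, primarily ligament reconstruction, will be withdrawn from the study." Neither section defines which surgery is significant or gives a time window. Randomisation takes place no later than the day of surgery (section 5.3), so the trigger falls after randomisation.

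**Data of withdrawn patients.** One paragraph before its withdrawal rule, section 5.3 says: "Data collected up to the date of withdrawal will be retained for analysis." Section 6.3 says that everything gathered before a patient's withdrawal is left out of the analysis and that "no further data collection will occur". The same section keeps the data of patients who are merely lost to follow-up.

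**Outcomes affected.** The primary outcome is pain at rest at day 7 (section 5.5.1). Table 2 continues pain at rest, pain on walking, Lysholm and WOMET to weeks 12 and 26. Section 8.3 plans a descriptive safety overview up to 26 weeks whose first item is "Readmitted to theatre and/or hospital".

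**Ligament injury.** The protocol summary gives as main exclusions, besides previous surgery on the index leg, "accompanying ligament injury, and advanced knee" osteoarthritis. Section 6.2.2 does not list ligament injury.

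**The concern.** A patient leaves the trial because of an event that occurs after randomisation and that may be related to treatment or to how the knee is doing. If the need for further surgery differs between arms, the patients who remain are no longer the groups that were randomised.

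Three things are at stake:

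- the primary comparison, if section 6.3 is followed and day-7 scores are deleted after the fact;
- the week 12 and week 26 comparisons, which lose patients selectively under either section;
- the readmission outcome, because one kind of event that it should count is also the event that ends participation.

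With two conflicting data rules in the protocol, the choice between them could also be made after the data have been seen.

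**Working it through.** The protocol states no re-operation rate or expected number of such withdrawals, so there is no figure to reproduce. The check is first a comparison of the two rules by timing of withdrawal, then an illustration on assumed inputs.

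**1. What is kept under each section**

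| Patient withdrawn for further surgery | Section 5.3 (keep data up to withdrawal) | Section 6.3 (exclude prior data, collect no more) |
|---|---|---|
| Before the day-7 score | Primary score never obtained; earlier data kept | Nothing kept |
| After day 7, before week 12 | Primary score kept; weeks 12 and 26 lost | Primary score deleted; nothing kept |
| Between weeks 12 and 26 | Primary and week 12 kept; week 26 lost | Primary and week 12 deleted; nothing kept |

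The sections therefore differ on the primary outcome for every patient withdrawn after day 7. They agree that late outcomes are lost. Section 6.3 also treats a patient who is re-operated less favourably than one who cannot be contacted, whose data stay in.

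**2. The readmission outcome.** Section 8.3 needs follow-up to 26 weeks. A return to theatre for significant surgery ends follow-up. Under 6.3 the patient's earlier data go as well. Under 5.3 the triggering surgery might or might not count as collected up to withdrawal, and any later readmission is not followed. Section 7.3 separately requires serious adverse events to be reported to the sponsor within one working day, and the section 7.2 definition includes inpatient hospitalisation, so some of these events would be on record. The protocol does not say that they feed the section 8.3 summary for withdrawn patients.

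**3. Illustration for day 7 if section 6.3 is applied.** From the protocol: 26 per arm and a target difference of 43 − 28 = 15 mm (section 6.1, Table 3). Assumed: *k* = 1 to 3 patients deleted from one arm only, with day-7 pain *D* = 10 to 30 mm above the rest of that arm.

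Mean of the full arm = mean of the rest + (k/26) × D, so deletion lowers the arm mean by (k/26) × D.

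- Smallest: (1/26) × 10 = 0.38 mm, or 0.38/15 = 2.6% of the target difference.
- Middle: (2/26) × 20 = 1.54 mm, or 1.54/15 = 10%.
- Largest: (3/26) × 30 = 3.46 mm, or 3.46/15 = 23%.

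Deletion from the Viscoseal arm would flatter Viscoseal; deletion from the control arm would count against it; equal deletion in both arms would largely cancel.

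**4. How many patients.** At assumed rates of 2%, 5% and 10%, the expected numbers among 52 are 1.04, 2.6 and 5.2, or about 1, 3 and 5 patients.

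**The case against.** **Data exclusion is not settled.** Section 5.3 keeps the data, and both data rules are worded for a patient's own withdrawal; neither expressly covers withdrawal by the study team. This stands. The defect is a contradiction, not a clear instruction to delete. But section 6.3 places the surgery rule under the same heading as the exclusion rule, so an analyst could reasonably apply it.

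**The safety outcome is not erased.** A reader might infer that re-operations disappear, so that 3 of 26 (11.5%) would be reported as 0 of 23. That would require every return to theatre to be significant surgery, section 6.3 to override 5.3, and serious adverse event reports to be ignored. The documents support none of these as a given. Hospital readmissions and lesser returns to theatre do not trigger withdrawal. Under-counting is possible; erasure is not shown.

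***Subsequently* is ambiguous.** It could include a ligament procedure found necessary at the index operation, which is not a readmission. On that reading the conflict with section 8.3 does not arise for those patients, but they would be withdrawn before day 7 and their primary score would be lost under either section.

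**Attrition is budgeted.** Section 6.1 allows 10% for withdrawal and loss to follow-up, so a loss of power from these withdrawals cannot be presented as new. This stands, and no power claim is made here. The allowance covers numbers, however, not selective removal.

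**Meniscectomy.** A reader might also infer selection in theatre: section 3.2.1 says "Patients are already randomised prior to surgery to avoid delays with surgery", meniscectomy is an exclusion in 6.2.2, and section 8.1 nevertheless records it among the procedures carried out. But the protocol nowhere says that eligibility is decided again in theatre or that converted patients are removed. Recording the procedure fits equally well with keeping them.

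**Conclusion.** The point holds in this form. The protocol withdraws patients on a post-randomisation event, gives two incompatible rules for their data, and ends follow-up in patients whose returns to theatre section 8.3 sets out to report to 26 weeks.

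The primary comparison is at risk mainly if section 6.3 is applied; under 5.3 only withdrawal before the day-7 score costs primary data. The week 12 and 26 outcomes and the readmission count are affected under either section.

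The size and direction of bias cannot be derived from the protocol. The range of 0.4 to 3.5 mm rests entirely on the assumed number, pain level and one-sidedness of the deletions. It shows that the effect could be anything from negligible to about a quarter of the target difference.

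The disagreement between the summary and section 6.2.2 on ligament injury is real but secondary. It matters because ligament reconstruction is the main named reason for withdrawal: someone working from 6.2.2 alone could randomise a patient who is later removed for it. The summary's own wording and the investigator-discretion criterion in 6.2.2 may prevent this in practice.

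**What to change.** 1. Reconcile sections 5.3 and 6.3 in one rule: data already collected from any randomised patient are retained and analysed in the arm to which the patient was randomised. State that the rule covers withdrawal by the study team as well as by the patient.
2. State that further surgery does not by itself end study follow-up and that data collection continues to week 26 unless the patient withdraws consent. Whether and when to operate remains a clinical matter outside this point.
3. State in section 8.3 that such surgery counts in the readmission outcome to 26 weeks, with serious adverse event reports as a source.
4. Make the protocol summary and section 6.2.2 agree on accompanying ligament injury. If it is meant as an exclusion, it should be assessed before randomisation and not dealt with by later withdrawal.

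The cost is a protocol amendment, with no visits beyond the existing schedule. Late scores recorded after a re-operation will add some noise; a sensitivity analysis that sets aside scores after further surgery can show whether this matters.

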5.5 Outcome measures

5.5.1 **Primary outcome measures**

To determine the level of index leg related pain experienced at day 7 post-operation and to compare the average pain scores of patients in the control and Viscoseal arm respectively, through administration of 100 mm visual descriptor scale (VDS) for pain at rest.

The study is powered to detect the established minimal clinically important difference (MCID) of 15 mm on a 100 mm VDS pain.

5.5.2 **Secondary outcome measures**

All the outcome measures are summarised in Table 2.

Table 2. Overview of measurements

Weeks	-12 weeks to day of surgery	48 hours	7 days*	14 days*	12 weeks#	26 weeks~
VDS pain scale for knee (at rest)	Х	Х	Х	Х	Х	Х
VDS pain scale for knee (walking)	Χ				Х	Χ
McGill pain questionnaire (at rest)	Х	X	X	Х		
Limb girth measurement (index leg)	X			Х	Х	
Lysholm scale	Χ				Χ	X
WOMET tool	Χ				Χ	Χ
Use of analgesics / anti- inflammatories	Х	X	Χ	Х	X	X
Patient satisfaction questionnaire re surgery						Χ
MRI scan (sub-study; not all participants)						Х

^{*} Allowed to be up to 2 days early or late

IRAS ref 272362 Page **13** of **30**

[#] Allowed to be up to 2 weeks early or late

[~] Allowed to be up to 4 weeks early or late

